- A combination of major and CRNM bleedings occurring during treatment or within 3 days of completing or interrupting or stopping study during the first 3-month treatment period.
- For subjects in Cohort 5, (ie,<6 months old), the primary safety endpoint is a combination of major and CRNM bleedings occurring during treatment or within 3 days of completing or interrupting or stopping study within 6 to 12 weeks + 3 days.
- All bleedings from first to the last dose + 30 days.
- A combination of major and CRNM bleedings from first to the last dose + 30 days.

Pharmacokinetic and Pharmacodynamic Endpoints:

Approximately, the first 12 subjects of each age cohort (total of approximately 53 to 60 subjects) randomized to the edoxaban treatment arm will participate in the multiple-dose PK/PD assessment on Day 5

Pharmacokinetics:

- Using population PK analysis, the following PK parameters will be estimated: apparent systemic clearance (CL/F) and apparent volume of distribution (V/F) of edoxaban.

Pharmacodynamics:

- The following biomarkers of coagulation will be estimated: PT, aPTT, anti-FXa for edoxaban treatment arm.

Planned Sample Size:	
This is an event driven trial and the total number of subjects randomized to treatment may be adjusted to ensure accumulation of 68 events in the mITT Analysis Set during the Main Treatment Period (Interim Analysis).
 
Assuming that the edoxaban group will observe a 24% reduction of the event rate relative to SOC and a non-inferiority margin of 1.5, then the study with 68 total primary endpoint events will have approximately 80% of power to demonstrate non-inferiority with alpha=0.05 (two sided). Assuming that 28% of event rate in the SOC-treatment group, 274 subjects, 137 subjects per treatment group, will be the randomization target for the study.

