2.1.2. Secondary Objectives

- To compare edoxaban against SOC with regard to the combination of major and clinically relevant non-major (CRNM) bleedings occurring during treatment or within 3 days of completing or interrupting or stopping study treatment during the first 3- month treatment period (for Cohort 5, the intended duration of treatment is at least 6 to 12 weeks).
- To compare edoxaban against SOC with regard to a combination of major and CRNM bleedings and symptomatic recurrent VTE, and death as result of VTE which occur from first to the last dose + 30 days.
- To compare edoxaban against SOC with regard to all bleedings which occur from first to the last dose + 30 days.
- To compare edoxaban against SOC with regard to the composite efficacy endpoint as described in the primary objective from randomization to the last dose + 30 days.
- To compare edoxaban against SOC with regard to all-cause mortality from randomization to the last dose + 30 days.
- To compare edoxaban against SOC with regard to the individual components of the composite efficacy endpoints as described in the primary objective during the first 3- month treatment period (for Cohort 5, the intended duration of treatment is at least 6 to 12 weeks).
- To compare edoxaban against SOC with regard to occurrence of DVT, catheter- related thrombosis, PE, sinovenous thrombosis within and after the first 3-month treatment period (for Cohort 5, the intended duration of treatment is at least 6 to 12 weeks).
- To compare edoxaban against SOC with regard to a composite combination of major and CRNM bleedings from first to the last dose + 30 days.
- To characterize the multiple dose pharmacokinetics of edoxaban in pediatric subjects at Day 5 using population pharmacokinetic (PK) analysis (apparent systemic clearance [CL/F] and apparent volume of distribution [V/F]) and to assess the effect of covariates such as age, body weight, and renal function on the PK of edoxaban.

- To evaluate the relationship between edoxaban exposure and safety (such as bleeding) and efficacy (thromboembolic events).
- To characterize the effect of edoxaban on biomarkers of coagulation (ie, PT, aPTT, and FXa).

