11.4.1.2. Secondary Efficacy Analyses

The following secondary efficacy analyses will be conducted:

- A composite endpoint, including symptomatic recurrent venous thromboembolic disease, death as result of VTE, and no change or extension of thrombotic burden from the randomization to the date of the last dose of study drug + 30 days, the same Cox proportional hazards regression model used for the primary efficacy analysis will be used. The time to first event is defined as the time (days) from the day of randomization to the first event experienced by a subject from the randomization to the date of the last dose of study drug + 30 days. Subjects who did not have a primary efficacy outcome during the study period will be censored at the last day the subject had a complete assessment for study outcomes or the last study drug + 30 days, whichever came first. These efficacy analyses will be based on mITT and PP Analysis Sets. The incidence of this composite endpoint will also be summarized by treatment arm for the mITT and PP Analysis Sets.
- Incidence of all-cause mortality from randomization to the date of the last dose of study drug + 30 days will also be summarized by treatment arm for the mITT Analysis Set.
- The incidence of each component (symptomatic recurrent venous thromboembolic disease, death as result of VTE, and no change or extension of thrombotic burden) of the composite primary endpoint occurred during the first 3 month treatment period will be summarized by treatment arm for the mITT and PP Analysis Sets.

- The occurrence of DVT, catheter-related thrombosis, sinovenous thrombosis, and PE during the first 3-month treatment period, after the 3 month treatment period will be summarized by treatment arm for the mITT Analysis Set

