11.6. Sample Size Determination

This is an event driven trial and the total number of subjects randomized to treatment may be adjusted to ensure accumulation of 68 events in the mITT Analysis Set during the Main Treatment Period.

The sample size calculation is based on statistical approach and results of Hokusai VTE study (DU176b-D-U305), a study of LMWH/edoxaban versus LMWH/warfarin in the treatment of acute VTE in adults. An NI margin of 1.5 (in hazard ratio) is used in the Hokusai VTE study and was aimed at preserving 70% of warfarin effect in adult population. A hazard ratio of 0.76 of recurrent VTE between edoxaban and warfarin for the first 3 months is also observed in Hokusai VTE study.

This pediatric study is designed to accumulate, approximately 68 overall primary efficacy events in the mITT Analysis Set during the Main Treatment Period. Assuming that edoxaban group will observe a 24% relative reduction to SOC arm, a total of 68 events will give approximately a power of 80% to demonstrate that LMWH/edoxaban is non-inferior to the comparator, considering a relative non-inferiority margin for the hazard ratio of 1.5 (two-sided $\alpha=0.05$).

Based on the completed clinical trials and literature review^{4, 14, 15, 16, 19, 22, 23, 24, 25}, we expect an incidence of composite primary efficacy endpoint of 28% in the control arm during the Main Treatment Period. Based on these estimates, 274 subjects (137 each arm) are expected to be randomized to study drug in order to accrue 68 primary efficacy events in the mITT Analysis Set during the Main Treatment Period.

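### The components of the primary composite are to be compared but are only tabulated by arm, and the adult margin of 1.5 is not justified for a composite that adds thrombotic burden

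*Combined protocol and SAP*

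**What the plan says.** **Objective.** Section 2.1.2, like the synopsis, sets this aim: "To compare edoxaban against SOC with regard to the individual components of the composite efficacy endpoints". Section 7.2 lists the three components (symptomatic recurrent VTE, death from VTE, thrombotic burden) as secondary endpoints.

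**Planned analysis.** For the incidence of each component, Section 11.4.1.2 provides only this: "composite primary endpoint occurred during the first 3 month treatment period will be summarized by treatment arm for the mITT and PP Analysis Sets". The plan asks for a Cox model elsewhere: for the composite to last dose + 30 days (11.4.1.2), the net clinical outcome (11.4.1.4) and bleeding (11.4.3.1). The components get none.

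**Margin.** Section 11.6 states: "An NI margin of 1.5 (in hazard ratio) is used in the Hokusai VTE study and was aimed at preserving 70% of warfarin effect". The next sentence gives the source of the assumed effect: "A hazard ratio of 0.76 of recurrent VTE between edoxaban and warfarin for the first 3 months is also observed". Section 11.4.1.1 then applies 1.5 to the pediatric composite, which adds burden that is unchanged or has extended on imaging.

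**Size.** "This pediatric study is designed to accumulate, approximately 68 overall primary efficacy events in the mITT Analysis Set". For the control rate, "we expect an incidence of composite primary efficacy endpoint of 28% in the control arm during the Main Treatment Period".

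**The concern.** There are two linked gaps. First, the analysis does not deliver what the objective promises: counts by arm are not a comparison with a stated uncertainty. Second, the margin and the assumed effect both come from an adult study, while the endpoint they are used on contains an imaging component. Sections 1.1 and 7.5 give a clinical reason for counting burden (its link to post-thrombotic syndrome). No section shows how much of the comparator's effect on burden, or on this composite, a ratio of 1.5 preserves.

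If burden supplies most of the events, the composite hazard ratio mainly reflects burden. A favourable burden result could then carry the composite below 1.5 while the ratio for recurrence or VTE death is unfavourable. The report would contain no prespecified interval for the clinical components, and readers might attach the 70% preservation to an endpoint for which it was never derived.

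**Working it through.** **1. The plan's own figures reproduce.** The inputs are a margin of 1.5, a true HR of 0.76, 1:1 allocation, two-sided alpha 0.05 and 80% power. Events = 4 × (1.96 + 0.8416)² / [ln(1.5/0.76)]² = 31.40 / 0.4623 = 67.9, so 68. With 28% on control and 28% × 0.76 = 21.3% on edoxaban, the mean rate is 24.64% and N = 68 / 0.2464 = 276. Under proportional hazards the edoxaban rate is 22.1% and N = 271. The stated 274 lies between these. The arithmetic of 11.6 is not in question.

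**2. What 1.5 allows on the composite.** 1 − (1 − 0.28)^1.5 = 1 − 0.611 = 38.9%, against 28% on control.

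**3. Share of burden in the 28%.** The protocol gives no split, so this is inferred.
- From the cited non-resolution rates (Sections 1.1 and 7.5): 14.8 / 28 = 53% and 18 / 28 = 64%. These series had mixed follow-up, from 5 days to several years, rather than 3 months.
- From the other side, using Section 1.1's 3-month recurrence rates (5.6% and 12.5%) and VTE mortality (0% to 2.2%): (28 − 5.6) / 28 = 80%, and (28 − 12.5 − 2.2) / 28 = 47.5%.

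A majority is likely, but not certain.

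**4. Can the composite pass with an unfavourable clinical ratio?** The scenarios are assumed. Each has 137 per arm and a control composite of 28%. The lower probability comes from simulated Cox fits without the age covariate, the higher from a binomial approximation.

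| Clinical, SOC vs edoxaban | Burden, SOC vs edoxaban | Composite HR | Non-inferiority declared |
|---|---|---|---|
| 10% vs 15% | 18% vs 9% | 0.84 to 0.86 | 65% to 69% |
| 5.6% vs 11.2% | 22.4% vs 13.4% | 0.86 to 0.89 | 59% to 65% |
| 5.6% vs 11.2% | 22.4% vs 17.0% | 1.01 to 1.04 | 36% to 40% |
| 10% vs 20% | 18% vs 9% | 1.04 to 1.10 | 28% to 36% |

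In the first row the clinical HR is ln(0.85)/ln(0.90) = 1.54, above 1.5.

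There is a limit on this effect. At 68 events the observed composite HR must be below 1.5 × exp(−1.96 × √(4/68)) = 0.93 to pass. Burden therefore has to improve enough to pull the whole composite below 1, not merely to 1.

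**5. Precision of the missing estimates.** The 95% CI for the clinical HR is the estimate divided and multiplied by exp(1.96 × 2/√events).
- Control rate 5.6%, HR 0.76: 137 × 0.056 × 1.76 = 13.5 events, factor 2.91.
- Control rate 10%, HR 0.76: 13.7 + 10.4 = 24.1 events, factor 2.2.
- Control rate 12.5%, HR 1: 137 × 0.125 × 2 = 34.2 events, factor 1.95.

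Power of a component test against 1.5 would be 24% to 46% at a true HR of 0.76 and 12% to 22% at 1. Reaching 68 recurrences at 0.76 would take about 620 to 1,380 subjects. For burden at an assumed 18% vs 13.7%, the half-width of the risk difference is 1.96 × √(0.18 × 0.82/137 + 0.137 × 0.863/137) = 8.6 percentage points. Estimation is feasible; a powered component test is not.

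**The case against.** **The components are reported, so nothing is hidden.** A reader might infer that the plan gives no estimate at all and would conceal an excess of recurrences. The documents do not support that. Section 11.4.1.2 requires component incidence by arm in both the mITT and PP sets, and tabulates DVT, PE, catheter-related and sinovenous thrombosis by arm. What is missing is a between-arm contrast with an interval.

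**An imaging-free endpoint is already modelled.** The net clinical outcome in Section 11.4.1.4 puts recurrent VTE and VTE death into the primary Cox model without burden. This is a real safeguard, but a partial one. It adds major and clinically relevant non-major bleeding, so fewer bleeds could offset more recurrences, and it runs from first dose to last dose + 30 days instead of the primary window.

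**The scenarios are chosen.** They need burden and recurrence to move in opposite directions, and nothing in the protocol suggests that they will. This stands: the table in the working shows possibility only.

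**The new interval might settle little.** Take SOC 10% clinical + 18% burden against edoxaban 16% + 12%. The composite HR is 1.0 and the clinical HR is ln(0.84)/ln(0.90) = 1.65, on 137 × 0.26 = 35.6 clinical events. Its 95% CI is about 0.86 to 3.2. This also stands, and it is why the analysis should be labelled supportive. An interval that wide is still more honest than bare counts.

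**A separate SAP may cover it.** Sections 11.4.3.6 and 11.7 defer detail to an SAP. No component contrast appears in the combined document. If one exists elsewhere, this part of the point falls away.

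**Conclusion.** The point holds in a limited form. The objective promises a comparison of components and the analysis section supplies only incidence by arm. The margin of 1.5 is carried over from adults with no justification for a composite that includes burden. Composite non-inferiority could therefore coexist with an unfavourable clinical-component ratio if burden improves. Under the assumed scenarios this happens in roughly 28% to 69% of trials, and no probability can be attached to the scenarios themselves.

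Three stronger readings are tempting and not supported:
- **That the 70% preservation was set on recurrent VTE.** Section 11.6 says only that the margin "was aimed at preserving 70% of warfarin effect in adult population". Recurrent VTE is named in the following sentence, about the 0.76. The link is an inference.
- **That the composite is almost all imaging.** The figures give an inferred majority of about 53% to 64%, resting on non-resolution rates from mixed follow-up.
- **That the primary test is invalid or the trial wrongly sized.** The 68 events and 274 subjects reproduce, and nothing here changes the decision rule.

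This is worth correcting because it is cheap and lets the trial answer its own objective.

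**What to change.** **Section 11.4.1.2 (and the matching synopsis text).** Replace the instruction to summarise the components with:
- an HR and two-sided 95% CI from the primary Cox model, over the primary window, for symptomatic recurrent VTE or death from VTE;
- a risk difference with 95% CI for the thrombotic burden component. State the denominator, because Section 7.1 assesses burden only in the absence of symptomatic recurrence.

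Label both as supportive estimation, with no margin and no test. Keep the incidence tables.

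**Section 11.6.** State that the 70% preservation was set in the adult study and have the sponsor name the endpoint it refers to. State that no preserved effect has been derived for the pediatric composite, and that 1.5 allows 28% to become about 38.9%. The text should not assert that the 70% refers to recurrent VTE unless the sponsor confirms it.

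**Cost.** Some wording and one or two tables. Margin, alpha and sample size stay as they are. The drawback is a wide clinical-component interval: the HR divided and multiplied by about 1.95 to 2.9 for assumed control recurrence rates of 12.5% down to 5.6%.

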3. STUDY DESIGN

3.1. Overall Design

This is an event driven Phase 3, prospective, randomized, open-label, blinded endpoint evaluation (PROBE) parallel group study in subjects with confirmed venous thromboembolism (VTE). A schematic representation of the study design is provided in [Figure 3.1](#). The parallel enrollment strategy schema in U157, U312 and between U157 and U312 is provided in [Figure 3.2](#).

Figure 3.1: Study Design

[figure not shown]
[figure not shown]

Figure 3.2: Enrollment Strategy Schema in U157, U312 and Between U157 and U312 Study

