3.2. Discussion of Study Design

This study is designed to evaluate the PK and PD of edoxaban and to compare the efficacy and safety of edoxaban with SOC in pediatric subjects with confirmed VTE.

The adjudication of the efficacy and safety endpoints will be conducted by a blinded adjudication committee.

The study includes two periods:

- The Main Treatment Period is defined as the time from randomization, until the end of Month 3 of treatment. The Main Treatment Period for subjects <6 months old (Cohort 5) is defined as the time from randomization until the end of anticoagulant therapy for at least 6 to 12 weeks.
 - Subjects who early discontinue the Main Treatment Period will be monthly followed according to the Schedule of Events (Table 17.1) through Month 3 visit (Visit 5), or earlier (unscheduled interim visit at 6 weeks) for subjects in Cohort 5, and 30-day Follow-Up Visit (Visit 9).

- Subjects who complete the Main Treatment Period but do not continue into the Extension Period will be followed for 30 days after last dose of study drug (Visit 9).
- The Extension Period is discretionary for the Investigator and will include treatment from the end of the Main Treatment Period (Month 3, Visit 5) up through the end of Month 12 (Visit 8).
 - Subjects who discontinue the treatment at any time after Month 3 will have a Month 12/Discontinuation Visit (Visit 8) performed with the subsequent 30 day follow-up (Visit 9).
 - Subjects who complete Extension Period treatment at Month 12 (Visit 8) will be followed for 30 days after last dose of study drug (Visit 9).
- Subjects who require anticoagulant treatment after discontinuation of the study treatment at any time will be transitioned to a therapy as determined by the Investigator.

The study will attempt to recruit at least 10% of the subjects diagnosed with pulmonary embolism.

About 274 subjects will be included in this randomized study (137 subjects in each treatment arm) which will be conducted at clinical sites located worldwide.

Randomization will be stratified by age cohorts and by region (US/Canada, Europe, Asia/Pacific, and Rest of the World). The total duration of the study is expected to be approximately 4.5 years.

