5.6. Subject Withdrawal or Discontinuation

Any subject who discontinues from the study treatment for any reason will have their study treatment discontinuation recorded. A subject may discontinue study treatment during the Main Treatment Period, however the subject should still remain as a study participant for scheduled visits through Month 3 (Visit 5) and the subsequent 30-day safety Follow-Up Visit.

Follow-Up Visit (visit 9) regardless if they stop all anticoagulant therapy or are placed on a treatment they have not been assigned at randomization. If a subject discontinues from treatment after Month 3, they should also be discontinued from the study and have a subsequent 30-day Follow-Up Visit.

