6.3.3.2. Month 2 (Visit 4) Procedures

- Record concomitant medications
- Count unused study drug tablets/ bottles/syringe and calculate compliance
- Dispense study drug medication and review dosing instructions
- Perform physical examination (see Section 9.10)
- Record vital signs (Section 9.9)
- Safety review for AEs/SAEs

- Review for endpoint events (VTE, bleeding)
 - The follow-up imaging performed if needed, must be always performed with the same modality as the initial diagnostic study

6.3.4. End of Main Treatment Period Visit (Month 3 or at least 6-12 weeks for Cohort 5, Visit 5) Procedures

All randomized subjects including those that have discontinued treatment will have an EOT assessment at Month 3 (within a ± 5 -day window).

The following will be performed at this visit:

- Perform physical examination (see Section [9.10](#))
- Vital signs (Section [9.9](#))
- Review concomitant medications
- Count unused study drug tablets/ bottles/syringe and calculate compliance
- Safety review for AEs/SAEs
- Review for endpoint events (VTE, bleeding)
 - Radiologic examination using the same diagnostic technique used at baseline to determine the thrombotic burden (see Section [7.1](#)).
 - VTE Radiologic Imaging (see Section [7.1](#)).
- Take samples for the following:
 - Liver function tests [ALT, AST, TBL, and ALP]
 - Serum creatinine
 - Hematology
 - Urine pregnancy test
- Dispense study drug medication and review dosing instructions per subject/parent's request and at the Investigator's decision to extend study treatment. After Month 3, the distribution of edoxaban or SOC may be for a 3-month period to align with the visit schedule, with the Sponsor's approval.

6.4. Extension Period (beyond Month 3 - Month 6, 9 and 12; Visits 6, 7, 8)

Per subject/parent's request and at the Investigator's decision, study treatment can be extended up to 12 months. At any time during the extended period, a subject can discontinue treatment and the study. In such a case a discontinuation study visit will be performed with a subsequent 30-day safety Follow-Up Visit (see [Table 17.1](#)).

The subjects on extended treatment will be followed for safety and efficacy assessment including bleeding events, recurrent VTE, and any treatment-related AEs at visit for Months 6 (Visit 6), 9 (Visit 7), and 12/ Discontinuation (Visit 8). Additionally, the subject will have a Follow-Up Visit (Visit 9) for safety assessment 30 days after treatment cessation. At Month

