11. STATISTICAL METHODS

11.1. Analysis Sets

Randomized Analysis Set will include all subjects who are randomized.

Safety Analysis Set will include all subjects in the Randomized Analysis Set who received at least one dose of study drug actually taken.

Modified ITT (mITT) Analysis Set will include all subjects in the Randomized Analysis Set who received at least one dose of randomized study drug.

Per-protocol (PP) Set will include all subjects in the mITT Analysis Set who are sufficiently compliant with the protocol. Criteria of sufficiently compliant will be detailed in SAP.

PK Analysis Set will include all subjects in the Safety Analysis Set who had at least one PK sample with measurable concentration.

PD Analysis Set will include all subjects in the Safety Analysis Set who had at least one measurable PD sample.

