11.2. General Statistical Considerations

All efficacy analyses will be based on the mITT Analysis Set or PP Analysis Set and will be performed based on the treatment arm assigned at randomization. All statistical tests will be two-sided at a 5% significance level, unless otherwise specified.

Safety analysis will be performed using the Safety Analysis Set. Subjects will be analyzed according to actual treatment received.

Unless otherwise specified, the baseline value of an efficacy variable for a subject is the last non-missing measurement before the first administration of study drug, and the baseline value of a safety variable is the last non-missing measurement before the first dose of the study drug.

In general, missing data will not be imputed for the purpose of data analysis. No visit windows will be used for analysis.

Continuous variables will be summarized by the number of observations, mean, standard deviation, median, and minimum and maximum values. Categorical variables will be summarized using frequency counts and percentages. Summary statistics will be presented by treatment arm.

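### After-Month-3 and whole-study summaries of four VTE event types use percentages over the full mITT set, although follow-up after Month 3 depends on an open-label choice to extend

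*Combined protocol and SAP*

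**What the plan says.** One secondary objective in section 2.1.2 is to compare the arms on DVT, catheter-related thrombosis, PE and "sinovenous thrombosis within and after the first 3-month treatment period". The matching analysis in section 11.4.1.2 is a summary by arm; for the later period the events "after the 3 month treatment period will be summarized by treatment arm for the mITT Analysis Set". The synopsis adds the whole study period.

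The denominator is fixed at the start of treatment: "Modified ITT (mITT) Analysis Set will include all subjects in the Randomized Analysis Set who received at least one dose of randomized study drug" (section 11.1). Being under observation after Month 3 is not a condition. Section 11.2 sets the form of the summary: "Categorical variables will be summarized using frequency counts and percentages". For these four event types the plan names no person-time rate, common window or time-to-event method.

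Section 3.1 describes a "prospective, randomized, open-label, blinded endpoint evaluation (PROBE) parallel group study", so parent and investigator know the arm. Section 3.2 says "The Extension Period is discretionary for the Investigator and will include treatment from the end of the Main Treatment Period", and section 6.4 says "Per subject/parent's request and at the Investigator's decision, study treatment can be extended up to 12 months". Subjects who finish the main period without extending are followed for 30 days after the last dose. For those who extend and then stop, section 5.6 says "If a subject discontinues from treatment after Month 3, they should also be discontinued from the study", with a further 30-day visit.

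**The concern.** The numerator grows with time observed, while the denominator is the same whether a subject is watched for one month or ten. Time observed after Month 3 is set by a choice made after randomization with knowledge of the arm. If that choice differs between a once-daily oral drug and a comparator of injections or INR-monitored VKA, the by-arm percentages mix the risk of an event with the amount of follow-up. A stated comparative objective would then be answered by a figure that can differ between arms when the risks do not, in whichever direction uptake differs.

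Intensity of detection may differ as well. Subjects in the extension have VTE imaging at the Month 12/Discontinuation visit (section 6.4.3). The 30-day follow-up of the others may be a telephone call (section 6.5.1).

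**Working it through.** **The plan's own figures.** The plan gives no figure for this item. Its primary sample size reproduces: 4 × (1.960 + 0.842)² / [ln(0.76/1.5)]² = 68 events for 80% power at two-sided 0.05. Nothing below changes it.

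**Follow-up after Month 3.** The synopsis gives total participation of 4 months at minimum and 13 at maximum, including 3 months of main treatment.
- Without extension: 4 − 3 = about 1 month.
- Full extension: 13 − 3 = about 10 months.

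**Assumed inputs.** The documents give neither extension uptake nor risk after Month 3. The illustration assumes:
- the same constant hazard λ in both arms, for extenders and non-extenders alike;
- 4% risk over 10 months, so λ = −ln(0.96)/10 = 0.00408 per month;
- a share f extending, observed for L = 10 months, and 1 month of observation for the rest;
- 137 subjects per arm (section 11.6).

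**Percentage over mITT** = f × (1 − e^(−λL)) + (1 − f) × (1 − e^(−λ)). The one-month risk is 1 − e^(−0.00408) = 0.407%.

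- 60% extending: 0.60 × 4% + 0.40 × 0.407% = 2.56%, or 137 × 2.56% = about 3.5 events.
- 30% extending: 0.30 × 4% + 0.70 × 0.407% = 1.49%, or about 2.0 events. Ratio about 1.73.
- 50% against 40%: 2.20% against 1.84%. Ratio about 1.19.
- Equal uptake: ratio 1.00.

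**Other assumed values**, with λ from 0.5% to 2% per month and L from 4 to 10 months:

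| Uptake | Range of ratio at equal hazard |
|---|---|
| 50% vs 50% | 1.00 |
| 60% vs 50% | 1.12 to 1.16 |
| 60% vs 40% | 1.27 to 1.39 |
| 70% vs 30% | 1.62 to 1.97 |

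**With person-time as denominator.** Expected subject-months are 137 × percentage / λ.
- 60% extending: 137 × 0.02563 / 0.00408 = about 860.
- 30% extending: 137 × 0.01485 / 0.00408 = about 498.
- Both rates equal λ, which is 0.00408 × 12 × 100 = 4.9 per 100 subject-years. Rate ratio 1.00.

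**With a common window.** Over the 30 days after Month 3, the expected percentage is 0.41% in each arm whatever the uptake.

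**The case against.** The strongest reply is that the plan already handles follow-up length where it models the data. Three analyses to last dose + 30 days use Cox regression:
- the efficacy composite, with explicit censoring (section 11.4.1.2, first item);
- the net clinical outcome, under the same model (section 11.4.1.4);
- bleeding, with explicit censoring (section 11.4.3.1).

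Symptomatic recurrent VTE is a component of the first two. A reader might infer that nothing in the plan allows for unequal follow-up beyond Month 3; these sections show otherwise. They do not settle the point, however. Both composites start at randomization or first dose and include other components, so neither isolates the four event types after Month 3.

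Second, section 11.3 requires drug exposure and study duration by arm, so unequal follow-up would be visible. That stands, but it does not correct the percentages. Section 11.7 leaves further detail to the SAP; no text available here addresses this item.

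Third, a reader might infer that edoxaban subjects will extend more. Section 1.1 suggests better satisfaction and adherence, but the documents forecast no uptake, and the comparator includes oral VKA. Direction and size are open.

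Fourth, a reader might take the ratio of uptakes as the bias (60/30 = 2.0; 50/40 = 1.25). That drops the month for which non-extenders are observed. Counting it gives about 1.73 and 1.19.

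Finally, person-time corrects length of follow-up only. It does not correct selection into the extension, differences in detection, or the mix of extenders on drug and non-extenders off it. If the hazard differs between those groups, uptake still shifts the rate. This stands and limits what the remedy can claim.

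**Conclusion.** The point holds for one descriptive item: the after-Month-3 and whole-study summaries of the four event types. As planned, their percentages depend on extension uptake and length as well as on risk. Under the stated assumptions the artefact is a ratio of about 1.73 for 60% against 30% uptake and about 1.19 for 50% against 40%. It is absent if uptake and length of extension match.

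The effect is one of expectation. A gap of about 3.5 against 2.0 events is within chance, so a trial could show no excess or the reverse. A reader might also infer that the efficacy conclusion is at risk; it is not. The item has no test or decision rule, and the 3-month primary analysis, the margin, the 68 events and the 274 subjects are untouched. The correction is worth making because a stated comparative objective rests on this summary and the change is cheap.

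**What to change.** In section 11.4.1.2 and the synopsis, for these four event types:

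1. Keep the crude percentages, and beside them report events per 100 subject-years of observation with 95% CI by arm, after Month 3 and over the whole study.
2. Add a summary over the window that nearly all subjects share, the 30 days after Month 3. State how it applies to Cohort 5, whose main period may end earlier, and to subjects who stop before Month 2, whose follow-up visit may be combined with Month 3 (section 5.6.1).
3. Show by arm the number entering the extension and their Month 3 scan result.
4. Label the after-Month-3 comparison as non-randomized and descriptive.

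Restricting the denominator to subjects seen beyond Month 3 is not needed. Nearly all have a 30-day visit, so the percentages would barely move. The bleeding analyses need no change.

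The cost is SAP wording and a few table columns, using dosing and visit dates already collected. The downside is that the comparison is openly reported as descriptive. Conduct and sample size do not change.
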